## 9 Safety Analyses

The SS will be used for all safety analyses. Summaries will be presented by treatment group and all TEV-48125 groups unless specified otherwise. Descriptive statistics will include number of subjects, mean, SD, median, minimum, and maximum.

### 9.1 Extent of Exposure

Data will be summarized for overall population and by country. Duration of treatment (days treated) is the number of days on treatment based on the first dose of IMP day and end of treatment (EOT) visit day/early withdrawal day (EOT visit day – first day of IMP + 1). For subjects who are lost to follow-up, the EOT date is defined as the last dose of IMP date + 27. The number of subjects receiving 1 dose, 2 doses, and 3 doses will be summarized. Duration of treatment (days) will be summarized using descriptive statistics and frequency distribution for the cumulative categories ( $> 0$  months,  $\geq 1$  month,  $\geq 2$  months,  $\geq 3$  months). One month will be defined as 28 days. The total exposure of IMP allocated at in each visit (V2/Baseline, V3/Month 1, and V4/Month 2) will also be summarized.

### 9.2 Adverse Events

All AEs will be coded by SOC and MedDRA PT. The incidence of the following events will be summarized:

- Treatment-emergent AEs (TEAEs)
- TEAEs by severity
- TEAEs with an outcome of death
- Serious TEAEs
- TEAEs leading to discontinuation of the IMP
- TEAEs reported in at least 2% of subjects in any treatment group

The above summaries will also be prepared for TEAEs potentially drug related, and for the overall population (SS) and by country. In addition, TEAEs will be summarized by age (<65, ≥65), sex and use of preventive migraine medication at baseline (yes, no).

- Injection site reaction TEAEs  
Injection site reaction AEs are determined by the investigator
- Ophthalmic TEAEs of at least moderate severity  
Ophthalmic AEs are defined as coded Eye disorders (10015919) by SOC.
- Drug-related Hepatic TEAEs  
Drug-related Hepatic AEs will be captured using the standardized MedDRA query (SMQ) Drug related hepatic disorders - comprehensive search (20000006).
- Anaphylaxis and severe hypersensitivity reaction TEAEs  
Anaphylaxis and severe hypersensitivity reaction AEs will be captured using the SMQ Hypersensitivity (20000214).
- Cardiovascular-related TEAEs  
Cardiovascular-related AEs will be captured using the SMQ Central nervous system vascular disorders (20000060), Cardiac arrhythmias (20000049), Cardiac failure (20000004), Cardiomyopathy (20000150), Ischaemic heart disease (20000043), Hypertension (20000147), Torsade de pointes/QT prolongation (20000001), and coded Vascular disorders (10047065) by SOC.
- Non-serious TEAEs reported in at least 5% of subjects in any treatment group

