- CT-8.5.2.1 Potentially Drug-related Serious TEAEs by MedDRA SOC and PT, All Countries (SS)
- CT-8.5.2.2 Potentially Drug-related Serious TEAEs by MedDRA SOC and PT in Japan (SS)
- CT-8.5.2.3 Potentially Drug-related Serious TEAEs by MedDRA SOC and PT in Korea (SS)
- CT-8.6.1.1 TEAEs leading to discontinuation of the IMP by MedDRA SOC and PT, All Countries (SS)
- CT-8.6.1.2 TEAEs leading to discontinuation of the IMP by MedDRA SOC and PT in Japan (SS)
- CT-8.6.1.3 TEAEs leading to discontinuation of the IMP by MedDRA SOC and PT in Korea (SS)
- CT-8.6.2.1 Potentially Drug-related TEAEs leading to discontinuation of the IMP by MedDRA SOC and PT, All Countries (SS)
- CT-8.6.2.2 Potentially Drug-related TEAEs leading to discontinuation of the IMP by MedDRA SOC and PT in Japan (SS)

CT-8.6.2.3	Potentially Drug-related TEAEs leading to discontinuation of the IMP by MedDRA SOC and PT in Korea (SS)
CT-8.7.1.1	TEAEs reported in at least 2% of subjects at Any Group by MedDRA SOC and PT, All Countries (SS)
CT-8.7.1.2	TEAEs reported in at least 2% of subjects at Any Group by MedDRA SOC and PT in Japan (SS)
CT-8.7.1.3	TEAEs reported in at least 2% of subjects at Any Group by MedDRA SOC and PT in Korea (SS)
CT-8.7.2.1	Potentially Drug-related TEAEs reported in at least 2% of subjects at Any Group by MedDRA SOC and PT, All Countries (SS)
CT-8.7.2.2	Potentially Drug-related TEAEs reported in at least 2% of subjects at Any Group by MedDRA SOC and PT in Japan (SS)
CT-8.7.2.3	Potentially Drug-related TEAEs reported in at least 2% of subjects at Any Group by MedDRA SOC and PT in Korea (SS)
CT-8.7.3.1	TEAEs by MedDRA SOC and PT in Age <65 years (SS)
CT-8.7.3.2	TEAEs by MedDRA SOC and PT in Age >=65 years (SS)
CT-8.7.3.3	TEAEs by MedDRA SOC and PT in Male (SS)
CT-8.7.3.4	TEAEs by MedDRA SOC and PT in Female (SS)
CT-8.7.3.5	TEAEs by MedDRA SOC and PT in using preventive migraine medication at baseline (SS)
CT-8.7.3.6	TEAEs by MedDRA SOC and PT in not using preventive migraine medication at baseline (SS)
CT-8.8.1	Injection Site Reaction TEAEs by MedDRA SOC and PT, All Countries (SS)
CT-8.8.2	Ophthalmic TEAEs of at least moderate severity by MedDRA SOC and PT, All Countries (SS)
CT-8.8.3	Drug-related Hepatic TEAEs by MedDRA SOC and PT, All Countries (SS)
CT-8.8.4	Anaphylaxis and severe hypersensitivity reaction TEAEs by MedDRA SOC and PT, All Countries (SS)
CT-8.8.5	Cardiovascular-related TEAEs by MedDRA SOC and PT, All Countries (SS)

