CT-8.8.6	Non-Serious TEAEs Greater Than or Equal to 5% in Any Group by MedDRA SOC and PT, All Countries (SS)
CT-9.1	Listing of Serious Adverse Events (SS)
CT-9.2	Listing of Adverse Events leading to discontinuation of the IMP (SS)
CT-9.3	Listing of Deaths (SS)
CT-9.4	Listing of Injection Site Reaction Adverse Events (SS)

CT-9.5	Listing of Ophthalmic Adverse Events of at least moderate severity (SS)
CT-9.6	Listing of Drug-related Hepatic Adverse Events (SS)
CT-9.7	Listing of Anaphylaxis and severe hypersensitivity reaction Adverse Events (SS)
CT-9.8	Listing of Cardiovascular-related Adverse Events (SS)
CT-10.1.1	Descriptive Statistics for Laboratory Values (Serum Chemistry) (SS)
CT-10.1.2	Descriptive Statistics for Laboratory Values (Hematology) (SS)
CT-10.1.3	Descriptive Statistics for Laboratory Values (Coagulation) (SS)
CT-10.1.4	Descriptive Statistics for Laboratory Values (Urinalysis) (SS)
CT-10.2.1	Incidences of PCS Abnormalities in Laboratory Tests (Serum Chemistry) (SS)
CT-10.2.2	Incidences of PCS Abnormalities in Laboratory Tests (Hematology and Coagulation) (SS)
CT-10.2.3	Incidences of PCS Abnormalities in Laboratory Tests (Urinalysis) (SS)
CT-10.3.1	Listing of PCS Abnormalities in Serum Chemistry Laboratory Tests (SS)
CT-10.3.2	Listing of PCS Abnormalities in Hematology and Coagulation Laboratory Tests (SS)
CT-10.3.3	Listing of PCS Abnormalities in Urinalysis Laboratory Tests (SS)
CT-10.4.1	Shift Table of Laboratory Values (Serum Chemistry) (SS)
CT-10.4.2	Shift Table of Laboratory Values (Hematology) (SS)
CT-10.4.3	Shift Table of Laboratory Values (Coagulation) (SS)
CT-10.4.4.1	Shift Table of Laboratory Values (Urinalysis1) (SS)
CT-10.4.4.2	Shift Table of Laboratory Values (Urinalysis2) (SS)
CT-11.1	Descriptive Statistics for Vital Sign and Weight Values (SS)
CT-11.2	Incidences of PCS Abnormalities in Vital Signs (SS)
CT-11.3	Listing of PCS Abnormalities in Vital Signs Values (SS)
CT-12.1	Descriptive Statistics for ECG Parameters (SS)
CT-12.2	Shift Table of ECG Findings (Investigators ECG Interpretation) (SS)
CT-12.3	Incidence of Categorical Changes in ECG Parameters (SS)
CT-12.4	Listing of Categorical Changes in Electrocardiogram Evaluations (SS)
CT-13.1	Injection Site Assessments - Injection-site Pain (SS)
CT-13.2	Injection Site Assessments - Injection-site Erythema (SS)
CT-13.3	Injection Site Assessments - Injection-site Induration (SS)
CT-13.4	Injection Site Assessments - Injection-site Ecchymosis (SS)

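### The safety category for anaphylaxis and severe hypersensitivity is filled by the whole Hypersensitivity SMQ, so its subject total and listing cover any grade under a title that says severe

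*SAP*

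**What the plan says.** Section 9.2 of the SAP lists several adverse event categories of particular interest, each with a rule for finding its events. For this one the whole rule is "Anaphylaxis and severe hypersensitivity reaction AEs will be captured using the SMQ Hypersensitivity (20000214"). The sentence mentions no grade, no seriousness condition, no separate anaphylaxis query and no case review.

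The same section states "All AEs will be coded by SOC and MedDRA PT" and plans a summary of "TEAEs by severity", so severity is held as an attribute of each event, separate from its coded term.

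Appendix 5 carries the category label unchanged into two outputs: table CT-8.8.4, "Anaphylaxis and severe hypersensitivity reaction TEAEs by MedDRA SOC and PT, All Countries (SS"), and CT-9.7, "Listing of Anaphylaxis and severe hypersensitivity reaction Adverse Events (SS").

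One other category in the list does carry a grade. Its heading is "Ophthalmic TEAEs of at least moderate severity", and the threshold is repeated in the titles of CT-8.8.2 and CT-9.5, the latter being "Listing of Ophthalmic Adverse Events of at least moderate severity (SS").

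**The concern.** The label and the selection rule describe different sets of events. The label announces anaphylaxis together with hypersensitivity that is severe. The rule takes every event whose preferred term belongs to a query named simply Hypersensitivity. A mild event coded to such a term would be counted in CT-8.8.4 and listed in CT-9.7 under the severe title.

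The category addresses a recognised risk of a subcutaneously injected product for which the trial also assesses antidrug antibodies (Sections 3.1, 3.2 and 5.1). A reader who wants the incidence of severe reactions by treatment group will turn to this table. Its category total would be the incidence of any hypersensitivity, so it would overstate severe reactions. Within that total, a difference between groups in the few severe events would be diluted by the milder ones.

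**Working it through.** The SAP gives no figure to reproduce and no arithmetic on rates applies. The check sets the rule beside its label, beside the neighbouring category, and beside the other planned outputs.

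**1. What the rule selects.** Events are coded to system organ class and preferred term. A standardised query selects on those codes. It does not read the severity recorded for the event. With no further condition, every TEAE with a term in the query enters the category, whatever its grade.

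**2. What the label promises.** Let *A* be the number of subjects in a group with at least one event in the query. Let *S* be the number with at least one event in the query that is graded severe or coded to an anaphylaxis term. Every subject in *S* is also in *A*, so *S* ≤ *A*. The literal rule makes the CT-8.8.4 total equal to *A*, while its title describes *S*. The excess is *A* − *S* ≥ 0: the subjects whose query events are all below severe and none of which is an anaphylaxis term. It is zero only if there are no such subjects.

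**3. The neighbouring category.**

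| | Ophthalmic | Hypersensitivity |
|---|---|---|
| Grade in the heading | at least moderate | severe |
| What the rule sentence defines | ophthalmic events, without the grade | the full label, including severe |
| Source of events | one system organ class | one SMQ |
| Appendix 5 titles | state the threshold | repeat the label |

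In the ophthalmic item the rule supplies the terms, and the heading adds a named threshold on the severity scale. In the hypersensitivity item the rule sentence takes the complete label, with the word severe in it, as its subject and equates it with the query. That leaves nothing for the heading to add.

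**4. Whether another output supplies *S*.**

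- CT-8.3.1.1 gives all TEAEs by severity, organ class and preferred term. It is not restricted to the query, and the SAP does not list the query's terms. Even with that list the rows cannot be added: a subject with severe events under two terms contributes 1 + 1 = 2 to the sum of rows but 1 to *S*.
- CT-8.5.1.1 gives serious TEAEs by preferred term and CT-9.1 lists serious events. They have the same limit, and they concern seriousness rather than severity.
- CT-8.8.4 is by preferred term, so an anaphylaxis term has its own row by treatment group. Its title announces no severity breakdown, so the other rows and the category total mix grades.
- CT-9.7 shows single events. Its columns are not described, so the SAP does not establish that severity appears there.

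No planned output gives *S*.

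**The case against.** The best counter-argument is that the ophthalmic threshold also sits in a heading and not in its definition sentence, and is nevertheless accepted as a filter. Read the same way, severe in the hypersensitivity heading would be the filter and the SMQ only the source of terms. That reading is possible, and it means the literal outcome is not certain. It does not rescue the text. Here the rule sentence itself equates the full label with the query, and if a filter is intended the SAP does not say whether it is severity grade, seriousness or both. Two programmers could produce different tables.

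The protocol, which is not at hand, may define this event or provide for case review. That also stands as a limit, but Section 9.2 does not refer to any such definition.

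Three stronger readings are tempting, and the documents do not support them.

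- *Anaphylaxis cannot be counted separately.* It can: CT-8.8.4 is by preferred term.
- *Severe reactions would be hidden.* An over-inclusive search loses no severe event that the query contains, and severe and serious events appear in CT-8.3.1.1, CT-8.5.1.1 and CT-9.1. The dilution concerns the category total only.
- *The error could create a false safety signal, or is known to be large.* Section 9 plans descriptive incidences without a safety test, and no event rate is given from which a number of misclassified subjects could be derived.

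**Conclusion.** The definition is wrong as written, with a limited reach. Taken literally, it gives one prespecified safety table a category total, and one listing a set of entries, that do not match their title. The direction is known: severe reactions would be overstated, not missed. The size is not known, because it depends on how many mild or moderate events are coded to the query and the SAP gives no basis for an estimate. The primary and secondary efficacy analyses are not affected.

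The conclusion rests on two things: the query is cited by its unqualified name, and selection is by coded term. The query's term list is not in the SAP and was not relied on. The correction should be made, because the table concerns a serious risk and the change is cheap.

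**What to change.** Title the unfiltered query Hypersensitivity (SMQ 20000214) in Section 9.2, CT-8.8.4 and CT-9.7. The label is then true of what the rule selects, and the any-grade count is kept.

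Add to CT-8.8.4 a row or severity breakdown that counts each subject once if any event in the query is graded severe or coded to an anaphylaxis preferred term. Add a severity column or flag to CT-9.7 on the same rule. List the anaphylaxis preferred terms in the SAP before unblinding. If the protocol already defines this category, Section 9.2 should cite that definition and use it.

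Retitling alone would remove the contradiction but would leave the number of subjects with severe events unreported. The full change needs one filter and a few words in the SAP. Adverse event severity is already recorded, so no new data are needed and no planned count is lost.

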### 9.3 Clinical Laboratory Data

Descriptive statistics will be calculated for clinical laboratory data and changes from baseline at each time point (V3/Month 1, V4/Month 2, V5/End of treatment [Month 3], and final evaluation).

Frequency distributions with the numbers and percentages of subjects with potentially clinically significant (PCS) values with any post-baseline (including unscheduled assessments and final evaluation) will be presented. The denominator for calculating the percentage of subjects will be the number of subjects with at least one post-baseline result for each test. Listing of subjects with PCS values will be prepared. The criteria are presented in [Appendix 3](#).

Shift tables (except qualitative urinalysis) will be created for baseline and post-baseline at each time point values classified into normal, high, or low based on the reference range.

Baseline will be the last value prior to the first dose of IMP. Each visit for post-baseline will be the Nominal visits. Final evaluation will be the last observed all post-baseline data

(including scheduled, unscheduled, and withdrawal visits). Summaries of PCS values will include all post-baseline data.

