#### **9.6 Electrocardiogram Data**

Descriptive statistics will be calculated for electrocardiogram (ECG) measurements and changes from baseline at each time point (V5/End of treatment [Month 3], additional visits for pharmacokinetic [at 3 to 10 days and at 14 to 21 days postdose at V2/Baseline, V3/Month 1, and V4/Month 2], and at final evaluation). Shift tables will be created for baseline vs post-baseline assessment results (normal, abnormal not clinically significant, or abnormal clinically significant) at final evaluation vs worst value.

For QTcB and QTcF, frequency distributions with the numbers and percentages of subjects will be presented for the following criteria:

- Subject who attains a value >450 msec post-baseline\*
- Subject who attains a value >480 msec post-baseline\*
- Subject who attains a value >500 msec post-baseline\*
- Increase in change from baseline value >30 msec at post-baseline\*
- Increase in change from baseline value >60 msec at post-baseline\*

\* “post-baseline” in the above criteria are at final evaluation and worst value.

The ECGs will be performed in triplicate. The average of the recorded measurements will be calculated for each visit. Baseline will be the last value prior to the first dose of IMP. Each visit for post-baseline will be the Nominal visits. Final evaluation will be the last observed all post-baseline data (including scheduled, unscheduled, additional visits for pharmacokinetic assessments, and withdrawal visits). Worst value will also be derived using all post-baseline data.

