### **9.8 Electronic Columbia-Suicide Severity Rating Scale**

Frequency distributions will be provided by response (positive/negative) for baseline and post-baseline scores. Post-baseline will include all post-baseline data, and if at least one time point is positive, post-baseline will be positive. Subjects having positive findings will be listed.

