**Appendix 3 Criteria for Identifying Laboratory Values of Potentially Clinically Significant**

Laboratory Tests	Criteria
Serum chemistry	
Alanine aminotransferase	$\geq 3 \times$ upper limit of normal
Aspartate aminotransferase	$\geq 3 \times$ upper limit of normal
Alkaline phosphatase	$\geq 3 \times$ upper limit of normal
Gamma glutamyl transferase	$\geq 3 \times$ upper limit of normal
Lactate dehydrogenase	$\geq 3 \times$ upper limit of normal
Urea Nitrogen	$\geq 30$ mg/dL
Creatinine	$\geq 2.0$ mg/dL
Total bilirubin	$\geq 2.0$ mg/dL
Coagulation	
International normalized ratio	$> 1.5$
Hematology	
Hematocrit	
Male	$< 37 \%$
Female	$< 32 \%$
Hemoglobin	

Laboratory Tests	Criteria
Male	≤ 11.5 g/dL
Female	≤ 9.5 g/dL
Leukocytes count	≤ 3,000 uL or ≥ 20,000/ uL
Eosinophils	≥ 10%
Neutrophils	≤ 1,000 uL
Platelet count	≤ 7.5 10  /uL or ≥ 70 10  /uL
Urinalysis	
Occult blood	≥ 2 units increase from baseline
Glucose	≥ 2 units increase from baseline
Ketones	≥ 2 units increase from baseline
Protein	≥ 2 units increase from baseline

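### Laboratory PCS tables (except urinalysis) and the absolute QTc categories count pre-existing abnormalities with new ones, and eC-SSRS is not specified as crossed with baseline, so no planned table gives a new-onset rate by arm

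*SAP*

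**What the plan says.** **Laboratory (Section 9.3, Appendix 3).** The numerator is any qualifying value after the first dose: "numbers and percentages of subjects with potentially clinically significant (PCS) values with any post-baseline (including unscheduled assessments and final evaluation) will be presented". The denominator is "The denominator for calculating the percentage of subjects will be the number of subjects with at least one post-baseline result for each test", and "Summaries of PCS values will include all post-baseline data". In Appendix 3 the chemistry, coagulation and hematology criteria are absolute limits, for example hematocrit below 32% in women or eosinophils of 10% or more. The four urinalysis criteria differ: each is defined as "≥ 2 units increase from baseline".

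**QTc (Section 9.6).** For QTcB and QTcF the first category is "Subject who attains a value >450 msec post-baseline", followed by the same for 480 and 500 msec, each at final evaluation and at worst value. Categories for increases above 30 and 60 msec stand beside them.

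**eC-SSRS (Section 9.8).** Positive and negative frequencies are given for baseline and for post-baseline; for the latter, "if at least one time point is positive, post-baseline will be positive". Subjects with positive findings are listed. No table of baseline against post-baseline is specified.

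**Other outputs.** Section 9.3 also plans laboratory shift tables ("Shift tables (except qualitative urinalysis) will be created for baseline and post-baseline at each time point values classified into normal, high, or low") and a PCS listing ("Listing of subjects with PCS values will be prepared"). Section 9.6 adds a shift table of ECG interpretation.

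**The concern.** A reader goes to these tables to see what arose on treatment. Appendix 5 titles CT-10.2.1 and CT-10.2.2 as incidences of PCS abnormalities, and CT-12.3 as the incidence of categorical ECG changes. Under the stated rule, a woman with a hematocrit of 31% before and after dosing counts as a PCS case, and so does a subject with eosinophils of 11% throughout. A subject whose QTc stays at 455 msec appears in a table titled as changes. Such subjects do not represent incidence or change.

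The rest of the SAP's safety reporting mostly looks at what is new. The adverse event summaries are of treatment-emergent events, and the urinalysis criteria are increases from baseline.

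What is at stake is legibility. Pre-existing cases raise the rate in every arm, pull the ratio between arms towards 1 and add noise to the comparison. The primary analysis is not touched.

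**Working it through.** The SAP gives no figure for these tables, so there is none to reproduce. The check has two parts.

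**1. Does any planned output give a new-onset rate by arm?**
- *Laboratory shift tables* classify by reference range, not by PCS limit. A subject below the reference range at baseline who later falls below the PCS limit moves from low to low. The tables are built by time point, so a PCS value at an unscheduled visit may enter the PCS count without appearing in a shift cell.
- *QTc increases above 30 and 60 msec* leave out a subject with a stable high QTc. They are not crossed with the absolute categories, so they do not show who newly passed 450, 480 or 500 msec.
- *The ECG shift table* (CT-12.2) uses the investigator's interpretation, not QTc category.
- *Listings* (CT-10.3.1, CT-10.3.2, CT-12.4, CT-13.5.2, PDATA-9) let a reader sort cases by hand but give no rate.
- *eC-SSRS margins* do not determine the cross-table. If, say, 5 of 180 were positive at baseline and 5 afterwards, the number of new positives could be anything from 0 to 5.

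The answer is no for all three domains.

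**2. How large is the effect?**

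Inputs:
- 180 subjects per group (SAP Section 4).
- Assumed: a share b already meets the criterion at baseline; a fraction q of these still meets it afterwards; new onset i among the rest is 1% on placebo and 4% on active. The SAP gives none of b, q or i.

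Formulas:
- Rate as planned: p = b·q + (1 − b)·i.
- Standard error of the difference as planned: √{[p0(1 − p0) + p1(1 − p1)]/180}.
- New cases only: rates of 1% and 4% among 180(1 − b) subjects per arm.

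Worked for b = 8%, q = 1:
- Placebo: 0.08 + 0.92 × 0.01 = 0.0892. Active: 0.08 + 0.92 × 0.04 = 0.1168.
- Ratio 0.1168/0.0892 = 1.31; difference 0.0276.
- SE = √[(0.0892 × 0.9108 + 0.1168 × 0.8832)/180] = 0.0320; difference/SE = 0.86.
- New cases only, n = 165.6: SE = √[(0.01 × 0.99 + 0.04 × 0.96)/165.6] = 0.0171; difference/SE = 0.03/0.0171 = 1.76; ratio 4.

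The same formulas with q = 1 give:

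| b | Placebo, as planned | Active, as planned | Ratio | Difference (points) | Difference/SE | New cases only: ratio | New cases only: difference/SE |
|---|---|---|---|---|---|---|---|
| 0% | 1.00% | 4.00% | 4.0 | 3.00 | 1.83 | 4.0 | 1.83 |
| 3% | 3.97% | 6.88% | 1.7 | 2.91 | 1.22 | 4.0 | 1.80 |
| 8% | 8.92% | 11.68% | 1.3 | 2.76 | 0.86 | 4.0 | 1.76 |

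Persistence of 80% (q = 0.8) gives a similar picture. The planned ratio is 2.7 at b = 1%, 1.6 at 5% and 1.3 at 10%, with risk differences of 2.97, 2.85 and 2.70 points.

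Difference/SE serves only as a yardstick for precision, since the SAP plans no test on these tables.

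**The case against.** The strongest reply is that the counting rule is openly stated, that safety is descriptive, and that the SAP surrounds these tables with other information: PCS and ECG listings, full data listings, change from baseline at each visit, shift tables, QTc increase categories and treatment-emergent adverse events by hepatic, arrhythmia and QT queries. Many cut-offs are also extreme (enzymes at three times the upper limit, creatinine of 2.0 mg/dL, QTc above 500 msec), so baseline prevalence may be close to zero for them, and there the two counts agree. Much of this stands, and it keeps the point minor. It does not supply a new-onset rate by arm.

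A reader might draw four stronger inferences that the documents do not support:
- *That all laboratory PCS tables are affected.* Urinalysis is not: an unchanged abnormality cannot meet a criterion defined as an increase.
- *That a new eC-SSRS positive cannot be identified.* CT-13.5.2 and PDATA-9 allow each positive subject to be classified. The layout of CT-13.5.1 is not shown either, so all that can be said is that the text specifies no crossing.
- *That new abnormalities are hidden.* The listings and change summaries show them, though not as a rate.
- *That the comparison between arms is biased in one direction.* Randomization spreads pre-existing cases evenly on average, and the risk difference barely moves.

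A further fair objection is that a table restricted to subjects not qualifying at baseline drops those who qualify and then worsen. That argues for adding to the present count, not replacing it.

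**Conclusion.** The point holds for chemistry, hematology and coagulation PCS and for the absolute QTc categories, where subjects who qualified before the first dose are counted with new cases. It holds for eC-SSRS only in that no cross-tabulation is specified. In each domain the planned tables lack a new-onset rate by arm.

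The rate in each arm is overstated as a measure of new abnormalities, and the ratio and precision are diluted. Under the assumptions above (new onset 1% and 4%, full persistence), the ratio falls from 4 to about 1.7 at 3% baseline prevalence and 1.3 at 8%, while the risk difference goes only from 3.0 to 2.8 points. At 0% there is no effect. Prevalence is not in the SAP and will differ by test, so these figures show a range and are not an estimate for this trial.

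Severity is minor. The point concerns descriptive safety reporting only and has no bearing on the efficacy conclusions.

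**What to change.** - **CT-10.2.1, CT-10.2.2 (Section 9.3) and CT-12.3 absolute categories (Section 9.6).** Keep the present any-post-baseline count and add a treatment-emergent line beneath it. Numerator: criterion met after the first dose and not met at baseline. Denominator: subjects with a baseline result and at least one post-baseline result who did not meet the criterion at baseline. A table of baseline category by worst post-baseline category would serve equally well.
- **Subjects who qualify at baseline and then worsen.** The retained line keeps them counted. Applied cut-off by cut-off, the added QTc lines also pick up a subject who moves from above 450 to above 480 msec. Where a laboratory test has one limit, the values remain in LAB-1 to LAB-3.
- **CT-13.5.1 (Section 9.8).** Specify a baseline (positive/negative) by post-baseline (positive/negative) table by arm.
- **CT-10.2.3 (urinalysis).** No change.

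The cost is some SAP wording, light programming and a few more table lines, using data already collected. The added line has a smaller denominator than the line above it, which should be footnoted.
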